#### 2.3.3 Medical History

Relevant medical histories and current medical conditions at baseline will be summarised separately by system organ class and preferred term, by treatment group. Histories of statin intolerance will be summarised by treatment group. FAS will be used for the analysis.

# 2.4 Treatments (study treatment, rescue medication, concomitant therapies, compliance)

All summaries of treatments will be performed on the Safety Set, unless otherwise specified.

#### 2.4.1 Study treatment / compliance

The number of study doses administered, duration of exposure, patient year of exposure will be summarized by treatment group. Listings will be provided.

The number of participants dosed will also be summarized by study visit and treatment group.

Duration of exposure for inclisiran arms will be calculated as: minimum of (Date of last dose of treatment – Date of first dose of treatment + 180, Date of last known visit – Date of first dose of treatment).

Duration of exposure for lipid lowering therapies will be calculated as: minimum of (Date of last dose of lipid lowering therapy – Date of first dose of lipid lowering therapy, Date of last known visit – Date of first dose of lipid lowering therapy).

Patient-year of exposure will be calculated as duration of exposure/365.25.

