5.1 Inclusion criteria

Participants eligible for inclusion in this study must meet **all** of the following criteria:

- 1. Signed informed consent must be obtained prior to participation in the study.
- 2. Male or female participants ≥ 18 years of age.
- 3. Patients on established lipid lowering medication, or have been recommended lipid lowering therapy by their health care provider but are unable to tolerate treatment.
- A total cholesterol measurement at screening that is ≥4 mmol/L [approximately 160 mg/dL].
- 5. Participants on lipid-lowering therapies should be on a stable dose for \geq 30 days before screening with no planned medication or dose change.

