8.3 Participant demographics/other baseline characteristics

Baseline demographic information will be collected during screening/baseline visit and will include age, sex and race/ethnicity. These data will be recorded in the eCRF.

Relevant medical and surgical history recorded within the last 5 years will be extracted from the EMR from the date of consent. (see Section 6.1.5 Table 6-2)

Concomitant medication taken within the last 5 years will be extracted from the participants' primary care EMR from date of consent.

Cardiovascular risk assessment

Information required to assess composite cardiovascular risk will include;

• Height - measured at screening/baseline visit and EOS visit

- Smoking status -collected at screening/baseline visit and EOS visit
- Dietary advice status -collected at screening/baseline visit and EOS visit
- Exercise status (calculated using Physical Activity Index (PAI) see Appendix 6) collected at screening/baseline visit and EOS visit

These data will be recorded in the eCRF.

• HbA1c- if available the closest recoded value prior to the screening/baseline visit and EOS visit to be extracted from the EMR.

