#### 2.4.2 **Prior**, concomitant and post therapies

Medications are collected through EMR and in this system medication end date is not available.

Lipid-lowering therapy use at screening and baseline/randomization visit (Day 1) will be summarized by treatment group. Lipid-lowering therapy newly added or changed after randomization will be summarized by treatment group.

| Novartis | Confidential | Page 15 of 37           |
|----------|--------------|-------------------------|
| SAP      |              | Study No. CKJX839A1GB01 |

Other medications will be listed and summarized according to the anatomical therapeutic chemical (ATC) classification system and preferred term, by treatment group.

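### The SAP's duration formula for lipid-lowering therapy has no defined end date, does not start on the study clock, and by default leaves out Group 1

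*SAP*

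**What the plan says.** SAP 2.4.1 plans duration of exposure and patient-years by treatment group. For LLT the rule reads "Duration of exposure for lipid lowering therapies will be calculated as: minimum of (Date of last dose of lipid lowering therapy" minus the first-dose date, compared with a second term that runs from the same first dose to the last known visit. The junction of the two terms reads "Date of first dose of lipid lowering therapy, Date of last known visit", so both subtract the same start date. Patient-years follow directly: "Patient-year of exposure will be calculated as duration of exposure/365.25".

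The next section, SAP 2.4.2, states: "Medications are collected through EMR and in this system medication end date is not available". SAP 5.1.3 imputes only the start dates of concomitant medications. It refers in passing to an imputed end date but gives no rule that would produce one.

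Two protocol provisions place LLT before the study. Section 5.1 requires stability before entry ("Participants on lipid-lowering therapies should be on a stable dose for" at least 30 days before screening). Section 8.3 sets the look-back: "Concomitant medication taken within the last 5 years will be extracted from the" primary care record.

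The population is set by the opening line of SAP 2.4: "All summaries of treatments will be performed on the Safety Set, unless otherwise specified". SAP 2.2 defines the Safety Set as participants with at least one dose of study treatment. The protocol glossary and Section 6.1 define study treatment as inclisiran. SAP 2.4.1 names no other population for the LLT rows.

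**The concern.** Three things go wrong if the formula is followed to the letter. The first term needs a date that the plan says its data source lacks. Both terms begin at a date that, for anyone already on LLT, lies before the trial. And the population excludes the arm whose only drug therapy is LLT.

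This matters for interpretation. The primary estimand (Protocol 12.4.1, SAP 2.5.1) is meant to capture the effect of changes in lipid-lowering medication. Behavioural support promotes adherence to prescribed medication in Groups 1 and 3 but not in Group 2 (Protocol 6.4.1), so persistence with LLT could differ by arm. A reader would look to the duration table for that. As specified, it mixes pre-study time with about nine study months, has no defined way to register stopping, and on a literal reading has no Group 1 column.

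**Working it through.** The documents state no exposure or patient-year figure, so there is nothing to reproduce. The check applies the SAP 2.4.1 formulas to the protocol timeline.

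**Inputs**
- Doses on Day 1 and Day 90 (Protocol 6.5.2). Last visit on Day 270, window 256 to 284 (SAP Table 2-1).
- Screening on Day -14 to Day -1 (Protocol 8.2), which is 1 to 14 days before Day 1.
- LLT stable for at least 30 days before screening (Protocol 5.1).
- Record look-back of 5 years from consent (Protocol 8.3), taken as 1,826 days with consent at screening.
- Assumptions: with no end date, the minimum falls to last visit minus first LLT dose. The pre-study start dates are illustrative values within the limits above.

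**Inclisiran formula, as a check**
- min(89 + 180, 269) = 269 days, and 269 / 365.25 = 0.74 patient-years. This matches the length of the study, so that formula behaves sensibly.

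**LLT formula, last visit on Day 270**

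| First recorded LLT dose | Days before Day 1 | Duration (days) | Patient-years | Ratio to 269 days |
|---|---|---|---|---|
| 30 days before screening | 31 to 44 | 300 to 313 | 0.82 to 0.86 | 1.12 to 1.16 |
| 1 year before screening on Day -14 | 379 | 648 | 1.77 | 2.41 |
| 5-year look-back limit | 1,827 to 1,840 | 2,096 to 2,109 | 5.74 to 5.77 | 7.79 to 7.84 |

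For 300 completers who all shared one start date, the total would run from 300 × 300 / 365.25 = 246 to 300 × 2,109 / 365.25 = 1,732 patient-years. On study it is 300 × 269 / 365.25 = 221. When the start year is missing, SAP 5.1.3 sets the start to one day before treatment, and the excess is then a single day.

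**Stopping**
- A participant who stops LLT on Day 90 has 89 on-study days. With no end date, even a formula starting at Day 1 would return 269 days: 269 / 89 = 3.0 times too long.

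**Population**
- Safety Set = at least one dose of study treatment; study treatment = inclisiran; Group 1 receives none. Taken together, a correctly treated Group 1 participant is not in the LLT exposure table.

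**The case against.** The strongest reply is that the rule is underspecified, which does not make it wrong. A missing end-date field does not rule out using the last issue or dispensing date as the last dose, and the SAP does not define first dose of LLT either. A programmer could adopt sensible conventions for both. That stands as far as it goes: a reader might infer that the figures are bound to be wrong, and the documents do not show that. The fall to the last visit is an assumption. But no such convention is written, and the text as it stands does not lead to one.

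A reader might also infer that this is the only planned look at background therapy. It is not. SAP 2.4.2 and Protocol 12.3 summarise LLT at screening and baseline, and LLT newly added or changed afterwards. New LLT is also a coded deviation (COMD01, SAP Table 5-4), and deviations are tabulated on the FAS (SAP 2.3.1). These show additions and changes; no stated rule lets them detect stopping without end dates. Protocol 6.4.1 would base adherence to standard of care on medications dispensed, but SAP 2.6 summarises the adherence endpoint only as PAM levels.

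The Safety Set problem comes from the analysis-set definition and touches every table run on that set. That is fair, but LLT duration is where Group 1 is most needed.

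Finally, the number feeds nothing else visible: the planned safety summaries are counts and percentages, with no exposure-adjusted rates. That is correct, and it limits how much weight the point can carry.

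**Conclusion.** The point holds as a minor one. As written, the first term of the LLT formula has no defined end date. Both terms count from a first dose that normally precedes the study for participants already on LLT. The default population leaves out Group 1. Participants who cannot tolerate LLT may have no duration to compute.

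The overstatement for a Day 270 completer runs from 12% to 16% at the eligibility minimum to nearly eight-fold at the look-back limit, on the assumption that the minimum falls to the last visit. The eight-fold figure is an upper limit and should not be read as typical, because no document gives the distribution of LLT start dates.

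A reader might conclude that the trial cannot judge whether background therapy stayed stable, or that the primary result is compromised. The documents do not support either. Other LLT summaries are planned, the primary estimand uses a treatment-policy strategy for background changes (SAP 2.5.3), and the exposure table is descriptive. The inclisiran formula, the primary analysis and the sample size are untouched. What is lost is a usable duration summary and a way to see stopping.

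**What to change.** In SAP 2.4.1:
- Start LLT exposure at randomisation (Day 1 in the SAP's convention), and cap it at the last known visit.
- Name the FAS for this summary, so that all three arms appear.
- Define the end as the last recorded on-study issue or dispensing date, if the extract holds it. Add days' supply only if quantity is held; the documents do not say that it is.
- If neither date is held, drop the LLT duration and patient-year rows and report by arm the proportion with an on-study LLT record.

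The cost is a few lines of SAP text and a small program change. No new visits or assessments are needed. The one thing to check first is which prescription fields the extract contains, because that decides between the last two options.

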#### 2.4.2 **Prior**, concomitant and post therapies

Medications are collected through EMR and in this system medication end date is not available.

Lipid-lowering therapy use at screening and baseline/randomization visit (Day 1) will be summarized by treatment group. Lipid-lowering therapy newly added or changed after randomization will be summarized by treatment group.

| Novartis | Confidential | Page 15 of 37           |
|----------|--------------|-------------------------|
| SAP      |              | Study No. CKJX839A1GB01 |

Other medications will be listed and summarized according to the anatomical therapeutic chemical (ATC) classification system and preferred term, by treatment group.

## 2.5 Analysis supporting primary objective(s)

The primary objective of this study is to demonstrate superiority of inclisiran +/- behavioural support compared to standard of care + behavioural support in a primary care setting, in adults with elevated LDL-C. Standard of care + behavioural support will be considered as control group as mentioned in section 1.1.

#### 2.5.1 **Primary endpoint(s)**

The primary endpoint is the percentage change in LDL-C from baseline to Day 270.

The primary estimand is defined as follows. The primary effectiveness question of interest is: What is the effect of the test treatment inclisiran versus control on change in LDL-C after 270 days of treatment in adults on established lipid lowering medication or who have been recommended lipid lowering therapy by their health care provider but are unable to tolerate treatment, regardless of treatment discontinuation for any reason and regardless of unforeseen change in the concomitant lipid lowering therapy.

The justification for the primary estimand is that it will capture both the effect of the study drug and the effect of changes in additional medication(s) used for lipid lowering, if they occur, in a primary care setting.

| The primary estimand | is described by the following attributes:  |
|----------------------|--|
| Population           | Adults with elevated LDL-C on established lipid lowering
medication or, have been recommended lipid lowering therapy by
their health care provider but are unable to tolerate treatment.   |
| Variable             | Percentage change in LDL-C from baseline to Day 270  |
| Treatment            | The randomised treatment (inclisiran alone or inclisiran with
behavioural support) as add-on to the control treatment of lipid-
lowering background therapy plus behavioural support, regardless of
treatment discontinuation for any reason and regardless of unforeseen
change in the concomitant lipid lowering therapy and regardless of
use of prohibited medications. |
| Summary measure      | Difference between treatments in mean percentage change in LDL-C from baseline to Day 270.   |
| Intercurrent events  | 
 
Study treatment discontinuation
 
Deviation in background treatment
 
Use of prohibited medications
 
  |

The primary estimand is described by the following attributes:

Patients who took extra dose of inclisiran (who are identified through EMR) during the study period will be excluded and additional analysis will be provided.

| Novartis | Confidential | Page 16 of 37           |
|----------|--------------|-------------------------|
| SAP      |              | Study No. CKJX839A1GB01 |

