12.4 Analysis of the primary endpoint(s)/estimand(s)

12.4.1 Definition of primary endpoint(s)/estimand(s)

The primary effectiveness question of interest is: What is the effect of the test treatment inclisiran (+/- behavioural support) and standard of care + behavioural support on change in LDL-C after 270 days of treatment in adults on established lipid lowering medication or who have been recommended lipid lowering therapy by their health care provider but are unable to tolerate treatment, regardless of treatment discontinuation for any reason and regardless of unforeseen change in the concomitant lipid lowering therapy.

The justification for the primary estimand is that it will capture both the effect of the study drug and the effect of changes in additional medication(s) used for lipid lowering, if they occur, in a primary care setting.

The primary estimand is described by the following attributes:

1. Population: Adults with elevated LDL-C on established lipid lowering medication or, have been recommended lipid lowering therapy by their health care provider but are unable to tolerate treatment. Further details about the population are provided in Section 5.

2. Endpoint: Percentage change in LDL-C from baseline to Day 270.

3. Treatment of interest: The randomised treatment (inclisiran alone or inclisiran with behavioural support) as add-on to the control treatment of lipid-lowering background therapy plus behavioural support. The type and dose of the concomitant lipid-lowering therapy should remain stable during the study. Further details about the investigational treatment and control treatment are provided in Section 6.

The summary measure: difference between treatments in least squares mean percentage change at Day 270.

The strategy for handling intercurrent events (treatment discontinuation, use of prohibited medications, deviation in background treatment or death) will be described in the SAP.

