#### 2.2 Analysis sets

Screened Set (SCR) will include all participants who provided study informed consent.

**Randomized set (RAN)** will consist of all participants who received a randomization number, regardless of whether study treatment received or not.

| Novartis | Confidential | Page 13 of 37           |
|----------|--------------|-------------------------|
| SAP      |              | Study No. CKJX839A1GB01 |

**Full Analysis Set (FAS)** will consist of all randomised participants with the exception of those mis-randomised participants who did not receive study drug. Mis-randomised participants are defined as not qualified for randomisation and are inadvertently randomised into the study. According to the intent to treat principle, participants will be analysed according to the treatment they have been assigned to during the randomisation procedure. The FAS will be used in analyses for the primary, secondary, **and the study** efficacy objectives.

**Safety Set (SAF)** will consist of all participants who received at least one dose of study treatment. Participants will be analysed according to the study treatment received. This will be the primary population for the safety analyses.

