#### 2.5.2 Statistical hypothesis, model, and method of analysis

The primary effectiveness objective of this study is to demonstrate superiority of each inclisiran arm compared to control in terms of the percentage change from baseline in LDL-C to Day 270 in adults with elevated LDL-C. The statistical hypotheses that will be tested for each inclisiran arm are as follows:

- $H_0$ : The difference between participants treated with inclisiran and control in the least squares mean percentage change from baseline to the Day 270 visit in LDL-C= 0
- $H_a$ : The difference between participants treated with inclisiran and control in the least squares mean percentage change from baseline to the Day 270 visit in LDL-C < 0

The primary objective will be achieved if null hypothesis  $(H_0)$  rejected at the one-sided significance level of 0.025.

The primary analysis will use an analysis of covariance (ANCOVA) model on the percent change in LDL-C from baseline to Day 270 to test the superiority of inclisiran over control after missing data imputation.

Due to probable heterogeneity of variances between treatment groups, ANCOVA model which assumes unequal variances for treatment group will be used. The model will include the fixed effects of treatment group with baseline LDL-C as a covariate.

Multiple imputation will be used to impute missing data using a washout model specified in Appendix 5.5.1. A total of 500 imputed datasets will be created. The ANCOVA model will be fitted to each imputed dataset, and results will be combined using Rubin's combination rules. The estimate and corresponding 2-sided 95% confidence intervals of mean difference between treatment groups will be calculated. p-value for hypothesis test for mean difference will also be provided. The FAS will be used for this analysis. The family-wise error rate for comparisons of the two inclisiran arms with the lipid-lowering background therapy plus behavioural support arm will be controlled using the Holm procedure.

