#### 2.5.3 Handling of intercurrent events

The approach of accounting for intercurrent events is as follows:

| Intercurrent
events (ICEs)         | Strategy and justification of handling ICEs  | Missing value imputation  |
|---------------------------------------|--|---|
| Study
treatment
discontinuation | Here interest is in effect of
treatment regardless of treatment
discontinuations due to any
reasons other than intercurrent
event. This event will be handled
using a treatment policy
strategy. | The LDL-C data collected post
discontinuation of study treatment
will be included in the analysis. If
there is no off-treatment data
available, then missing data on Day
270 or after treatment
discontinuation will be imputed
using missing not at random
(MNAR) for inclisiran arms and
using missing at random (MAR) |

Primary estimand:

| Intercurrent
events (ICEs)           | Strategy and justification of handling ICEs   | Missing value imputation  |
|---|---|---|
|   |   | approach for placebo arm participants.  |
| Deviation in
background
treatment | Interest is in effect of treatment
regardless of substantial changes
to background therapy during
study treatment. This will be
handled with a treatment policy
strategy . | The LDL-C data collected after
deviation in background treatment
will be included in the analysis.
Missing values will be imputed in
same way as mentioned in Appendix
5.5.1 |
| Use of
prohibited
medications     | Interest is in effect of treatment
regardless of changes in
concomitant lipid lowering
medication during study treatment.
This will be handled with a
treatment policy strategy . | The LDL-C data collected after
deviation in background treatment
will be included in the analysis.
Missing values will be imputed in
same way as mentioned in Appendix
5.5.1 |

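### SAP 2.5.1 excludes participants with an extra inclisiran dose without naming the analysis; read literally, this conflicts with the FAS-based, treatment-policy primary analysis

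*SAP*

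**What the plan says.** The sentence closes SAP 2.5.1, below the table that sets out the primary estimand: "Patients who took extra dose of inclisiran (who are identified through EMR) during the study period will be excluded and additional analysis will be provided".

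The surrounding plan says the following.

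- **Estimand.** SAP 2.5.1 asks for the effect "regardless of treatment discontinuation for any reason and regardless of unforeseen change in the concomitant lipid lowering therapy". The treatment attribute adds that it also applies whatever the "use of prohibited medications". Protocol 12.4.1 justifies this choice because "it will capture both the effect of the study drug and the effect of changes in additional medication(s) used for lipid lowering".
- **Intercurrent events.** SAP 2.5.1 lists three: stopping study treatment, deviating from background therapy, and prohibited medication. SAP 2.5.3 ("The approach of accounting for intercurrent events is as follows") assigns treatment policy to all three and keeps the LDL-C values collected afterwards. An extra inclisiran dose is not listed.
- **Analysis set.** Under SAP 2.2 the FAS "will consist of all randomised participants with the exception of those mis-randomised participants who did not receive study drug", and "According to the intent to treat principle, participants will be analysed according to the treatment they have been assigned to during the randomisation procedure". For the primary ANCOVA, SAP 2.5.2 says "The FAS will be used for this analysis".
- **Exclusion table.** SAP Table 5-4 marks exclusion from the FAS for INCL01A, INCL01B, OTH03 and TRT02 only. None of these concerns an extra dose.

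**The concern.** An extra dose found in the medical record during the study is a post-randomisation event. Dropping participants because of it means the arms compared are no longer the arms that were randomised.

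It may also be related to outcome. Protocol 6.1.4 ties prescribing after the study to whether the investigator judges that the patient has benefited. The phase III schedule in Protocol 1.1.4 included a dose at Day 270, which is also the target day of this trial's endpoint. The end-of-study window in SAP Table 2-1 runs to Day 284, and the disputed sentence does not say when its study period ends. With a loose cut-off, a participant could be removed for a dose given after the primary LDL-C sample had already been taken.

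Two analysts could therefore apply the SAP in good faith and report different primary estimates. Allocation is open label, and Section 5.6 allows the exclusion table to be updated until shortly before database lock, so the rule should be settled in advance.

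**Working it through.** **1. Comparison of the text.** There are two readings.

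| Reading | Consequence | Fit with the rest of the SAP |
|---|---|---|
| Literal: these participants are excluded, and a further analysis is also given | The primary analysis runs on the FAS minus extra-dose participants | Conflicts with 2.2, 2.5.2 and Table 5-4. Conflicts with 2.5.3 if off-study inclisiran counts as prohibited medication |
| Mild: an additional analysis omits them | The primary analysis is unchanged | Consistent, but 2.5.5 and 2.5.6 define no such analysis |

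On the condition in the first row: Protocol 6.1.5 bars adding drugs prescribed to lower LDL-C, or anything taken to lower lipids. The drugs it names are examples. Inclisiran is not among them, but off-study inclisiran fits the category.

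**2. The plan's own sample size.** Inputs from SAP Section 3: effect size 0.3, one-sided alpha 0.025, power 90%, drop-out 20%.

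- n per arm = 2 × (1.960 + 1.282)² / 0.3² = 234 evaluable after rounding up.
- 234 / (1 − 0.20) = 293 after rounding up. This is within 3% of the stated 300, so the figure is reproduced.
- Evaluable at the planned size: 300 × 0.80 = 240 per arm.

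**3. Precision and power for LDL-C.** Inputs from SAP Section 3: SD 30 (control) and 20 (inclisiran), difference 10 points.

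- Standard error = √(30²/240 + 20²/240) = √5.417 = 2.33 points.
- Power = Φ(10/2.33 − 1.960) = 99.0% at one-sided 0.025. At 0.0125, the first Holm step, it is 98.0%.
- Dropping 1% of an inclisiran arm (238 left) leaves 98.0% at 0.0125. Dropping 10% (216 left) gives a standard error of √(30²/240 + 20²/216) = 2.37 and power of 97.6%.

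**4. Shift in the estimate.** If a fraction p of an arm is dropped and its mean differs from the remainder by d points, the arm mean moves by −p × d. The documents give neither p nor the d used in the first scenario, so both are assumptions.

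*Inclisiran arm, d = ±10 to ±20 points:*

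- p = 1%: 0.01 × 10 to 0.01 × 20 = 0.1 to 0.2 points.
- p = 10%: 0.10 × 10 to 0.10 × 20 = 1 to 2 points.
- The direction depends on whether the dropped participants did better or worse than the rest of their arm.

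*Control arm, off-study inclisiran, d = −50 points.* This is the rounded phase III difference from Protocol 1.1.4.1 (52 and 50 points), taken as fully expressed at Day 270:

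- p = 1%: 0.01 × 50 = 0.5 points.
- p = 5%: 0.05 × 50 = 2.5 points.
- p = 10%: 0.10 × 50 = 5 points.
- Dropping these controls raises the control mean and so enlarges the estimated effect. These are upper values, because a late or single dose would have less than the full effect.

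For scale, 2.5 points is 2.5 / 2.33 = about 1.1 standard errors.

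**The case against.** The strongest reply is that the sentence never says the exclusion is from the primary analysis or the FAS. Its second half can be taken to mean that an additional analysis will leave these participants out. The FAS definition, the statement that the ANCOVA uses the FAS, and the absence of an extra-dose row in Table 5-4 all support that as the likelier intent. Position is weak evidence too, since text around the estimand table is displaced in this copy. All of this stands, so a reader who infers that the SAP plainly removes these participants from the primary analysis goes further than the text allows. What it does not remove is the ambiguity: the words still state an exclusion, and the additional analysis remains undefined.

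Second, extra dosing is not a listed intercurrent event, so a direct clash with treatment policy exists only if it counts as prohibited medication. Otherwise the fault is a missing event and a missing strategy. This stands.

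Third, an extra dose most naturally means one beyond the two scheduled in Protocol 6.5.2, and so concerns Groups 2 and 3. A reader might infer that the rule removes control cross-overs and inflates the effect. The documents do not establish that. They give no cross-over rate, the wording does not name Group 1, and in the inclisiran arms the shift could go either way. The control scenario is included only because the sentence does not rule that arm out.

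**Conclusion.** Wrong as written, on the literal reading. On the milder reading, it is an unspecified analysis. In either case the sentence leaves open the analysis, the arms, the meaning of an extra dose and the end of the relevant period.

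The size is conditional on assumed proportions: about 0.1 to 2 points in either direction if 1 to 10% of an inclisiran arm is dropped, and up to 0.5, 2.5 or 5 points of inflation if 1, 5 or 10% of controls had off-study inclisiran with the full effect.

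It would be tempting to conclude that the trial's main claim is in danger. The documents do not support that. Power for a 10-point difference stays near 98% at the first Holm step, and the phase III differences in Protocol 1.1.4 were 48 to 52 points at Day 510. What is at stake is which effect is estimated and whether the estimate rests on the randomised groups.

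**What to change.** Make three edits to the SAP before database lock.

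1. In 2.5.1, replace the sentence with: *All FAS participants remain in the primary analysis regardless of inclisiran received outside the assigned schedule, in any arm (treatment policy).*
2. Add inclisiran outside the assigned schedule to the intercurrent events in 2.5.1 and 2.5.3. Keep the LDL-C values observed afterwards, as for the three events already listed.
3. In 2.5.6, define the exclusion as a supplementary analysis only. State the arms it covers, what counts as an extra dose and how the record is searched for it, and the date cut-off relative to the participant's Day 270 sample.

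Report the number of affected participants by arm alongside that analysis.

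Treatment policy is an estimand choice, but it is the one the SAP already makes for every event it lists. The cost is one sentence, one new intercurrent-event entry and a short paragraph. No new data collection is needed, because the SAP already plans to identify these participants from the medical record.
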